#### **2.4. Study Design**

This is a single institution, non-randomized, single arm, open-label study for the doublet epacadostat and pembrolizumab. The primary purpose of this protocol is treatment, designed to evaluate one or more interventions for treating a disease, syndrome or condition.

#### **2.5. Correlative Studies Background and Rationale**

Blood and tissue will be collected for future correlative studies and stored at Stanford. For further information, see Section 9.0

- Blood: Plasma, and PBMC will be collected every three weeks for correlative studies.
- Tissue: Pre and on-treatment (day 42 ± 5 days) tissue biopsies will be collected for correlative studies.

### **3. PARTICIPANT SELECTION AND ENROLLMENT PROCEDURES**

For entry into the study, the following criteria must be met. Please refer to Appendix A for the eligibility and verification checklist to assist with patient enrollment.

### **3.1. Subject Population**

Subjects with metastatic or recurrent distal esophageal (within 5 cm of the GEJ), GEJ, or gastric adenocarcinoma who have had disease progression on at least one prior therapy or be intolerant to that therapy if they have not progressed. If the patient is HER2 + they must have received Herceptin (trastuzumab). At Stanford Cancer Institute (SCI) there will be 30 patients enrolled over the recruitment period.

### **3.2. Inclusion Criteria**

In order to be eligible for participation in this study, the subject must meet all of the following:

- 3.2.1. Age  $\geq$  18 years of age on day of signing informed consent.
- 3.2.2. Be willing and able to provide written informed consent/assent for the study
- 3.2.3. Histologically or cytologically confirmed adenocarcinoma of the distal esophagus, gastroesophageal junction or stomach, including patients with HER2+ disease. Distal esophagus is defined as within 5 centimeters of the GEJ.
- 3.2.4. Patients must have metastatic or unresectable disease, including those with HER2+ disease.
- 3.2.5. Must have progressed on at least one line of prior therapy for metastatic disease, or be intolerant to that therapy if they have not progressed, and for HER2+ disease should have received prior trastuzumab.
- 3.2.6. Life expectancy  $\geq$  12 weeks
- 3.2.7. Have a performance status of 0 or 1 on the ECOG Performance Scale.
- 3.2.8. Have measurable disease per RECIST v1.1, assessed within 4 weeks prior to study entry.
- 3.2.9. Tumor deemed amenable to biopsy by core for metastatic site or endoscopic biopsy for primary tumor (for both before and on-treatment biopsies).
- 3.2.10. Patient must be willing to undergo two biopsies - before and on-treatment, provided the procedure is not deemed high-risk and is clinically feasible.
- 3.2.11. Demonstrate adequate organ function as defined in **Table 1**, all screening labs should be performed within 7 days of treatment initiation.

**Table 1: Adequate Organ Function Laboratory Values**

System	Laboratory Value
Hematological	
Absolute neutrophil count (ANC)	$\geq$ 1,500 /mcL
Platelets	$\geq$ 100,000 / mcL
Hemoglobin	$\geq$ 9 g/dL or $\geq$ 5.6 mmol/L without transfusion or EPO dependency (within 7 days of assessment)
Renal	
Serum creatinine OR Measured or calculated a creatinine	$\leq$ 1.5 X upper limit of normal (ULN) OR

clearance (GFR can also be used in place of creatinine or CrCl)	≥60 mL/min for subject with creatinine levels > 1.5 X institutional ULN
Hepatic	
Total bilirubin	≤ 1.5 X ULN OR Direct bilirubin ≤ ULN for subjects with total bilirubin levels > 1.5 ULN
AST (SGOT) and ALT (SGPT)	≤ 2.5 X ULN OR ≤ 5 X ULN for subjects with liver metastases
Albumin	≥2.5 mg/dL
Coagulation	
International Normalized Ratio (INR) or Prothrombin Time (PT)	≤1.5 X ULN unless subject is receiving anticoagulant therapy as long as PT or PTT is within therapeutic range of intended use of anticoagulants
Activated Partial Thromboplastin Time (aPTT)	≤1.5 X ULN unless subject is receiving anticoagulant therapy as long as PT or PTT is within therapeutic range of intended use of anticoagulants
a Creatinine clearance should be calculated per institutional standard.	

- 3.2.12. Female subject of childbearing potential should have a negative urine or serum pregnancy within 3 days prior to receiving the first dose of study medication. If the urine test is positive or cannot be confirmed as negative, a serum pregnancy test will be required.
- 3.2.13. Female subjects of childbearing potential must be willing to use an adequate method of contraception starting with the date of consent through 120 days after the last dose of study medication. *Note: Abstinence is acceptable if this is the usual lifestyle and preferred contraception for the subject.*
- 3.2.14. Male subjects of childbearing potential must agree to use an adequate method of contraception starting with the date of consent through 120 days after the last dose of study therapy. *Note: Abstinence is acceptable if this is the usual lifestyle and preferred contraception for the subject.*
- 3.2.15. Must be able to swallow pills.

### 3.3. Exclusion Criteria

The subject must be excluded from participating in the study if the subject:

- 3.3.1. Is currently participating and receiving study therapy or has participated in a study of an investigational agent and received study therapy or used an investigational device within 4 weeks of the first planned dose of treatment.
- 3.3.2. Has known hypersensitivity to pembrolizumab and/or Epacadostat or any of their excipients.
- 3.3.3. Has had a prior anti-cancer monoclonal antibody (mAb) within 4 weeks prior to study Day 1 or who has not recovered (i.e.,  $\leq$  Grade 1 or to baseline) from adverse events due to agents administered more than 4 weeks earlier. Note that denosumab for treatment for bone metastases is allowed.
- 3.3.4. Has had prior chemotherapy, targeted small molecule therapy, or radiation therapy within 2 weeks prior to study day 1 or who has not recovered (i.e.,  $\leq$  Grade 1 or to baseline) from adverse events due to a previously administered agent.
- *Note:* Subjects with  $\leq$  Grade 2 neuropathy are an exception to this criterion and may qualify for the study.

- *Note:* If subject received major surgery, they must have recovered adequately from surgery prior to starting therapy.
- 3.3.5. Have been treated on any Merck-sponsored pembrolizumab-containing gastric cancer pivotal trial will require prior authorization by Merck in order to enroll in this study.
- 3.3.6. Has had prior therapy with IDO-inhibitors
- 3.3.7. Has active autoimmune disease that has required systemic treatment in the past 2 years (i.e. with use of disease modifying agents, corticosteroids or immunosuppressive drugs). Replacement therapy (e.g., thyroxine, insulin, or physiologic corticosteroid replacement therapy for adrenal or pituitary insufficiency, etc.) is not considered a form of systemic treatment.
- 3.3.8. Has known history of, or any evidence of active, non-infectious pneumonitis
- 3.3.9. Has received a live vaccine within 30 days of planned start of study therapy.
- Note: Seasonal influenza vaccines for injection are generally inactivated flu vaccines and are allowed; however, intranasal influenza vaccines (e.g., Flu-Mist®) are live attenuated vaccines, and are not allowed.*
- 3.3.10. Has known active central nervous system (CNS) metastases and/or carcinomatous meningitis. Subjects with previously treated brain metastases may participate provided they are stable (without evidence of progression by imaging for at least four weeks prior to the first dose of study treatment and any neurologic symptoms have returned to baseline), have no evidence of new or enlarging brain metastases, and are not using steroids for at least 7 days prior to study treatment. This exception does not include carcinomatous meningitis which is excluded regardless of clinical stability. Patient with prior CNS metastases treated w/ prior RT will also need all of the following: A. 2 months off RT before starting study or 4 weeks following XRT if MRI is stable and the patient is off steroids, B. Baseline MRI with no edema, and C. stable for at least 8 weeks.
- 3.3.11. Has known additional malignancy that has progressed or requires active treatment. Exceptions include basal cell carcinoma of the skin, squamous cell

- carcinoma of the skin, or in situ cervical cancer that has undergone potentially curative therapy.
- 3.3.12. Has active infection requiring systemic therapy
- 3.3.13. Has a known history of active TB (Bacillus Tuberculosis)
- 3.3.14. Has known active Hepatitis B (e.g., HBsAg reactive) or Hepatitis C (e.g., HCV RNA [qualitative] detected)
- 3.3.15. Has a diagnosis of immunodeficiency or is receiving systemic steroid therapy or any other form of immunosuppressive therapy within 7 days prior to the first dose of study medication
- 3.3.16. Has a known history of Human Immunodeficiency Virus (HIV) (HIV 1/2 antibodies)
- 3.3.17. Is pregnant or breastfeeding, or expecting to conceive or father children within the projected duration of the study, starting with pre-screening or screening visit through 120 days after the last dose of study treatment
- 3.3.18. Has had monoamine oxidase inhibitors within 21 days before screening
- 3.3.19. Has any history of serotonin syndrome after receiving 1 or more serotonergic drugs
- 3.3.20. Has presence of a gastrointestinal condition that may affect drug absorption
- 3.3.21. Use of systemic corticosteroids
- 3.3.22. Has history or presence of an abnormal electrocardiogram (ECG) which, in the investigator's opinion, is clinically significant.
- QTcF > 480 ms or presence of a Left Bundle Branch Block (LBBB). If the QRS duration > 120ms, the JTc can be used in place of the QTcF. The JTc must be < 340 ms.
- 3.3.23. Has history or current evidence of any condition, therapy, or laboratory abnormality that might confound the results of the study, interfere with the subject's participation for the full duration of the study, or is not in the best interest of the subject to participate, in the opinion of the treating investigator.
- 3.3.24. Has known psychiatric or substance abuse disorders that would interfere with cooperation with the requirements of the study.

3.3.25. Has known allergy or reaction to any component of either study drug or formulation components.

#### **3.4. Informed Consent Process**

All participants must be provided a consent form describing the study with sufficient information for participants to make an informed decision regarding their participation. Participants must sign the IRB approved informed consent prior to participation in any study specific procedure. The participant must receive a copy of the signed and dated consent document. The original signed copy of the consent document must be retained in the medical record or research file.

The granting of informed consent must be documented in writing, using an ICF that contains all the elements required by ICH E6 and describes the nature, scope, and possible consequences of the study in a form understandable to the study subject.

Subjects of childbearing potential must agree to take appropriate measures to avoid pregnancy in order to participate in the study.

#### **3.5. Randomization Procedures**

This is an open-label single-arm study, therefore, the investigator and subject will know the treatment administered and there is no randomization.

#### **3.6. Study Timeline**

##### **3.6.1. Primary Completion**

The study is expected to reach its accrual goal within 18 months from the time enrollment begins. Patients are anticipated to stay on treatment for 6 months. Thus, primary completion will take approximating 6 months from date of last patient enrolled. Upon completion of the last patient's last treatment, all patients will remain in long-term follow-up for evaluation of survival.

##### **3.6.2. Study Completion**

Patients will be followed for progression and survival. Estimated study completion is approximately 4 years from when study opens.

### **4. TREATMENT PLAN**

#### **4.1. Study Procedures**

The schedule of events calendar (Section 9) summarizes the study procedures to be performed at

each visit. Individual study procedures are described in detail below. It may be necessary to perform these procedures at unscheduled time points if deemed clinically necessary by the investigator. Furthermore, additional evaluations/testing may be deemed necessary by the investigator and/or Merck and Incyte for reasons related to subject safety. In some cases, such evaluation/testing may be potentially sensitive in nature (e.g., HIV, Hepatitis C, etc.), and thus local regulations may require that additional informed consent be obtained from the subject. In these cases, such evaluations/testing will be performed in accordance with those regulations.

#### **4.2. Duration of Treatment and Subject Participation**

Each subject enrolled in the study will continue receiving combination study treatment in continuous 21-day cycles for up to 24 months, and then treatment with monotherapy epacadostat may continue as long as the subject is receiving benefit from treatment and has not had disease progression or met any criteria for study withdrawal. If the subject discontinues all study treatment, the treatment phase will end, and the subject will enter the follow-up phase. Study participation is expected to average about 6 months.

#### **4.3. Screening Phase**

##### **4.3.1. Informed Consent**

The screening phase will be up to 28 days. Screening is the interval between the signing of the informed consent document and the day the subject receives the first dose of treatment on the study (Cycle 1 Day 1). Informed consent must be obtained before performing any study-specific procedures. Assessments that are required to demonstrate eligibility may be performed over the course of 1 or more days during this phase.

##### **4.3.2. General Informed Consent**

Consent must be documented by the subject's dated signature or by the subject's legally acceptable representative's dated signature on a consent form along with the dated signature of the person conducting the consent discussion.

A copy of the signed and dated consent form should be given to the subject before participation in the study.

The initial informed consent form, any subsequent revised written informed consent form and any written information provided to the subject must receive the IRB/ERC's approval/favorable opinion in advance of use. The subject or his/her legally acceptable representative should be informed in a timely manner if new information becomes available that may be relevant to the subject's willingness to continue participation in the study. The communication of this information will be provided and documented via a revised consent form or addendum to the original consent form that captures the subject's dated signature or by the subject's legally authorized representative's dated signature.

Specifics about a study and the study population will be added to the consent form template at the protocol level.

The informed consent will adhere to IRB/ERC requirements, applicable laws and regulations.

#### **4.3.3. Inclusion/Exclusion Criteria**

All inclusion and exclusion criteria will be reviewed by the investigator or qualified designee to ensure that the subject qualifies for the study prior to starting them on the study.

Results from the screening visit evaluations will be reviewed to confirm subject eligibility before enrollment or the administration of study drug. Tests with results that fail eligibility requirements may be repeated once during the screening phase if the investigator believes the results to be in error. Additionally, a subject who fails screening may repeat the screening process 1 time if the investigator believes there has been a change in eligibility status (e.g., after recovery from an infection).

#### **4.3.4. Demographics and Medical History**

Demographic data and a complete medical and medication history will be collected at screening by the investigator or qualified designee and will include date of birth, race, ethnicity, medical and surgical history, and concurrent illnesses assessed using the NCI CTCAE v5. Medical history should include all active conditions, and any condition diagnosed within the prior 10 years that are considered to be clinically significant by the investigator. Details regarding the disease for which the subject has enrolled in this study (e.g., date of diagnosis, primary tumor histology, prior systemic therapies, surgeries, radiation therapy, and stage of cancer) will be recorded separately and not listed in medical history.

#### 4.3.5. **Prior Medications**

The investigator or qualified designee will review prior medication use, including any Protocol-specified washout requirement, and record prior medication taken by the subject within 28 days before starting the study. Treatment for the disease for which the subject has enrolled in this study will be recorded separately and not listed as a prior medication.

#### 4.3.6. **Concomitant Medications**

The investigator or qualified designee will record medication, if any, taken by the subject during the study. Concomitant medications include any prescription, over-the-counter, or natural/herbal preparations taken or administered during the study period. All medications related to reportable SAEs and AEs should be recorded.

All clinical, efficacy and laboratory procedures and assessments that will be administered at screening phase and treatment cycles are listed below.

#### 4.3.7. **Disease Details and Treatments**

##### 4.3.7.1. **Disease Details**

The investigator or qualified designee will obtain prior and current details regarding disease status.

##### 4.3.7.2. **Prior Treatment Details**

The investigator or qualified designee will review all prior cancer treatments including systemic treatments, radiation therapy, and surgeries.

##### 4.3.7.3. **Subsequent Anti-Cancer Therapy Status**

The investigator or qualified designee will review all new anti-neoplastic therapy initiated after the last dose of study treatment. If a subject initiates a new anti-cancer therapy within 30 days after the last dose of study treatment, the 30-day Safety Follow-up visit must occur before the first dose of the new therapy. Once new anti-cancer therapy has been initiated, the subject will move into survival follow-up.

#### **4.4. Treatment Phase**

The treatment period with the combination therapy will continue every 21 days for up to 24 months. Single agent epacadostat may continue indefinitely beyond 24 months provided the patient has benefit.

##### **4.4.1. Administration of Investigational Products**

Study treatment should be administered on day 1 of each cycle (21 day cycles) after all procedures/assessments have been completed as detailed in the schedule of events calendar. Study treatment may be administered up to 3 days before or after the originally scheduled day 1 of each cycle due to administrative reasons. All study treatments will be administered on an outpatient basis.

##### **4.4.2. Treatment Compliance**

Treatment compliance with all study-related medications should be emphasized to the subject by the site personnel, and appropriate steps should be taken to optimize compliance during the study. Subjects will bring all bottles of unopened, empty, and unused epacadostat drug with them to each study visit. Investigative site staff will perform a count of returned tablets to assess compliance, and this information will be entered into the electronic case report form (eCRF).

###### **4.4.2.1. Epacadostat (INCB024360)**

Site staff will dispense medication sufficient for a 3-week cycle (21 days). Subjects will be administered study drug at 300 mg oral, twice daily, continuous dosing. All twice daily doses of epacadostat will be taken orally in the morning and evening, approximately 12 hours apart without regard to food. If the morning or evening dose is missed by more than 4 hours, that dose should be skipped and the next scheduled dose should be taken at the usual scheduled time. Doses of epacadostat will be self-administered except on the day of the cycle that the patient is visiting the study clinic for infusion (Day 1 of each cycle); epacadostat will be taken prior to pembrolizumab infusion.

Epacadostat compliance will be calculated based on the drug accountability documented and monitored by the site staff (tablet counts and pill diary). The objective is 100% compliance and investigators and their staff should evaluate compliance at each visit, and take appropriate steps to optimize compliance. If the subject falls below 85% compliance, based on 2 subsequent visits,

then it will need to be addressed immediately, and could be means to remove the subject from the study.

Epacadostat will be given daily in combination with pembrolizumab every 3 weeks for up to 24 months provided subjects are receiving benefit from treatment and have not had disease progression or met any criteria for study withdrawal. Intrasubject escalation of epacadostat is not permitted. Single agent epacadostat may be continued beyond 24 months provided the patient has benefit.

Subjects will receive treatment in continuous 21 day cycles; however, treatment may include temporary interruptions to allow for resolution of certain toxicities. Interruptions from the protocol-specified treatment plan for > 12 weeks between epacadostat and pembrolizumab doses due to toxicity require consultation between Merck/Incyte and the investigator and written documentation of the collaborative decision on subject management.

#### 4.4.2.2. **Pembrolizomab (MK-3475)**

Pembrolizumab 200 mg will be administered as a 30-minute intravenous (IV) infusion every 3 weeks ( $\pm$  3 days) and will make every effort to target infusion timing to be as close to 30 minutes as possible. However, given the variability of infusion pumps, a window of -5 minutes and +10 minutes is permitted (i.e., infusion time is 30 minutes -5 min/+10 min).

Pembrolizumab may be administered through a peripheral line or indwelling catheter. Intrasubject dose escalation of pembrolizumab is not permitted.

The total volume of study treatment infused will be compared to the total volume prepared to determine compliance with each dose administered.

Whenever possible, the lowest infusion rate should be used that will allow completion of the infusion within 30 minutes. Maximum rate should not exceed 6.7 mL/min through a peripheral line or indwelling catheter, however when necessary to infuse a larger volume (i.e. 250 mL), the flow rate may go as high as 10 ml/min (maximum) in order to keep the infusion within the window as defined above. Use 30 mL normal saline to flush the infusion line at the end of the infusion. Do not co-administer other drugs through the same infusion line.

See Appendix F which contains specific instructions for the preparation of the pembrolizumab infusion fluid and administration of infusion solution.

#### **4.5. End of Treatment**

If a decision is made that the subject will permanently discontinue study drug, the end of treatment visit should be conducted approximately 30 days after the last dose of study medication.

When a subject discontinues/withdraws prior to study completion, all applicable activities scheduled for the final study visit should be performed at the time of discontinuation. Any AEs which are present at the time of discontinuation/withdrawal should be followed in accordance with the safety requirements outlined in Section 7. Subjects who a) attain a CR or b) complete 24 months of treatment with pembrolizumab and epacadostat may discontinue treatment with the option of restarting treatment in the future if/when they meet the criteria specified in Section 4.8. After discontinuing treatment following assessment of CR, these subjects should return to the site for a Safety Follow-up Visit (described in Section 4.6.1) and then proceed to the Follow-Up Period of the study (described in Section 4.6.2).

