#### **4.6. Follow-Up Phase**

##### **4.6.1. Safety Follow-Up Visit**

The mandatory Safety Follow-Up Visit should be conducted approximately 30 days after the last dose of study treatment or before the initiation of a new anti-cancer treatment, whichever comes first. All AEs that occur prior to the Safety Follow-Up Visit should be recorded. Subjects with an AE of Grade > 1 will be followed until the resolution of the AE to Grade 0-1 or until the beginning of a new anti-neoplastic therapy, whichever occurs first. SAEs that occur within 30 days of the final dose on the study or before initiation of a new anti-cancer treatment should also be followed and recorded. Subjects who are eligible for retreatment with pembrolizumab (as described in Section 4.8) may have up to two safety follow-up visits, one after the Treatment Period and one after the Second Course Phase.

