##### **4.6.2. Follow-Up Period**

Subjects who discontinue study treatment for a reason other than disease progression will move into the Follow-Up Phase and should be assessed every 9 weeks ( $\pm$  7 days) by radiologic

imaging to monitor disease status. Every effort should be made to collect information regarding disease status until the start of new anti-neoplastic therapy, disease progression, death, end of the study or if the subject begins retreatment with pembrolizumab as detailed in Section 4.8, Second Course Phase. Information regarding post-study anti-neoplastic treatment will be collected if new treatment is initiated.

Subjects who are eligible to receive retreatment with pembrolizumab according to the criteria in Section 4.8, Second Course Phase (Retreatment Period), will move from the Follow-up Phase to the Second Course Phase when they experience disease progression.

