#### 4.6.3. **Survival Follow-Up**

Once a subject experiences confirmed disease progression or starts a new anti-cancer therapy, the subject moves into the survival follow-up phase and should be contacted by telephone every 12 weeks (~ 3 months) to assess for survival status until death, withdrawal of consent, or the end of the study, whichever occurs first.

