#### 4.12. Subject Withdrawal/Discontinuation Criteria

Subjects may withdraw consent at any time for any reason or be dropped from the study at the discretion of the investigator should any untoward effect occur. In addition, a subject may be withdrawn by the investigator or the Sponsor if enrollment into the study is inappropriate, the study plan is violated, or for administrative and/or other safety reasons.

A subject must be discontinued from the study for any of the following reasons:

- The subject or legal representative (such as a parent or legal guardian) withdraws consent.
- Confirmed radiographic disease progression
  - Note:* For unconfirmed radiographic disease progression, please see Section 10.
  - Note:* A subject may be granted an exception to continue on treatment with confirmed radiographic progression if clinically stable or clinically improved
- Unacceptable adverse experiences
- Intercurrent illness that prevents further administration of treatment
- Investigator's decision to withdraw the subject
- The subject has a confirmed positive serum pregnancy test
- The subject is lost to follow-up
- Completed 24 months of uninterrupted treatment with pembrolizumab or 35 administrations of study medication, whichever is later.

*Note:* 24 months of study medication is calculated from the date of first dose. Subjects

who stop pembrolizumab after 24 months may be eligible for up to one year of additional study treatment if they progress after stopping study treatment provided they meet the requirements detailed in Section 4.8.

- Administrative reasons

The EOT and Follow-up visit procedures are listed in Section 9 (Study Calendar) and Section 4 (Visit Requirements). After the end of treatment, each subject will be followed up to 30 days or until new anti-cancer treatment is initiated, whichever occurs first for adverse event monitoring, including SAEs. Subjects who discontinue for reasons other than progressive disease will have post-treatment follow-up for disease status until disease progression, initiating a non-study cancer treatment, withdrawing consent or becoming lost to follow-up. After documented disease progression each subject will be followed by telephone for overall survival until death, withdrawal of consent, or the end of the study, whichever occurs first.

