### 6.2. Dose Modifications of Pembrolizumab and Epacadostat

AEs (both non-serious and serious) associated with pembrolizumab and epacadostat exposure may represent an immunologic etiology. These adverse events may occur shortly after the first dose or several months after the last dose of treatment. Based on existing clinical trial data, most irAEs were reversible and could be managed with interruptions of pembrolizumab and

epacadostat, administration of corticosteroids and/or other supportive care. For suspected irAEs, ensure adequate evaluation to confirm etiology or exclude other causes. Based on the severity of irAEs, withhold or permanently discontinue pembrolizumab and epacadostat and administer corticosteroids. Dose modification and toxicity management guidelines for irAEs associated with pembrolizumab are provided in **Table 4**.

See Sections 4.10.4 for additional supportive care guidelines, including use of corticosteroids if necessary. Patients requiring treatment with corticosteroids for irAEs should be held through completion of taper, unless otherwise discussed and approved by Merck and Incyte.

In case toxicity does not resolve to Grade 1 within 12 weeks after last dose of study treatment should be discontinued only after consultation with Merck and Incyte. With investigator and Merck and Incyte agreement, subjects with a laboratory AE still at Grade 2 after 12 weeks may continue treatment in the study only if asymptomatic and controlled.

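### No TSH is scheduled at the end-of-treatment visit, so patients who stop for progression have none after their last Day 1 visit: a cheap improvement

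*Combined protocol and SAP*

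**What the plan says.** On timing, Section 4.5 states that "the end of treatment visit should be conducted approximately 30 days after the last dose of study medication". For a subject who discontinues or withdraws before study completion, its next paragraph adds that "all applicable activities scheduled for the final study visit should be performed at the time of discontinuation". Section 4.6.1 gives a second visit the same nominal date: "The mandatory Safety Follow-Up Visit should be conducted approximately 30 days after the last dose of study treatment", or before new anti-cancer treatment if that comes first. Section 4.3.7.3 repeats that "the 30-day Safety Follow-up visit must occur before the first dose of the new therapy".

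Section 4.12 sends staff to Sections 9 and 4 for the procedures. Each Section 9 calendar has eight columns. The three after the Day 1 visits are EOT (labelled as the discontinuation visit, window + 5 days, no anchor date), Follow-Up Visits every 9 weeks, and Survival Follow-Up every 12 weeks. Footnote 15 of the first-course calendar requires TSH at every Day 1 visit, with T3 and fT4 only if TSH is abnormal or the patient has symptoms.

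On who attends, Section 4.6.2 says: "Subjects who discontinue study treatment for a reason other than disease progression will move into the Follow-Up Phase". After confirmed progression or the start of new therapy, Section 4.6.3 says that "the subject moves into the survival follow-up phase and should be contacted by telephone every 12 weeks".

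On late events, Section 6.2 says: "These adverse events may occur shortly after the first dose or several months after the last dose of treatment". Section 6.3 repeats the point. The thyroid note in Table 4 asks for monitoring at the start, periodically on treatment, and when clinically indicated.

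**The concern.** Asymptomatic thyroid change is found only if TSH is measured. The plan measures it about every three weeks on treatment and again at the 9-week follow-up visits. It skips the one clinic visit that patients leaving for progression still attend, although blood is already drawn there for other tests.

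At stake is a small part of safety monitoring. Adverse events are followed for up to 30 days after treatment or until new therapy (Section 4.12), and safety is a secondary objective (Section 1.2). Within that window, a silent thyroid abnormality in a patient who stopped for progression could go unseen and unrecorded, and the patient could start the next therapy without anyone knowing of it.

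**Working it through.** The plan gives no figure to reproduce on this point. The check is a reading of the calendars, a tracing of who attends which visit, and a day count.

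**1. Is the blank cell real?** The laboratory rows, which are marked alike in both calendars, are:

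| Row | Screening or progression | Day 1 columns (4) | EOT | Follow-Up | Survival | Marked, of 8 |
|---|---|---|---|---|---|---|
| Chemistry | X | 4 | X | X | – | 7 |
| Hematology | X | 4 | X | X | – | 7 |
| Lipid panel | X | 4 | X | – | – | 6 |
| Urinalysis | X | 4 | X | – | – | 6 |
| Endocrine | X | 4 | – | X | – | 6 |

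Every row has eight fields. The endocrine row skips EOT and is marked again at Follow-Up, whereas lipid and urinalysis do the reverse. A shifted column would not produce that pattern twice, so the blank is not a table-reading artefact.

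**2. Scheduled TSH after the last Day 1 visit, by route off treatment**
- Stops for a reason other than progression: next TSH at the first 9-week visit, 63 ± 7 = 56 to 70 days after discontinuation.
- Stops for another reason but starts new therapy before that visit: moves to survival follow-up (4.3.7.3, 4.6.3), so 0.
- Stops for confirmed progression: EOT (no TSH), then telephone contact, so 0.
- Stops on progression not yet confirmed: no 9-week visit is clearly assigned.

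**3. Does the answer depend on when EOT takes place?**
- If EOT is the 30-day Safety Follow-Up Visit, the EOT column applies and has no TSH.
- If EOT is at discontinuation and the 30-day visit is separate, EOT has no TSH, the 30-day visit has no column, and 4.6.1 lists no laboratory tests.

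The count for patients who stop for progression is 0 either way.

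**4. What would a TSH at about day 30 add?** Time from the last Day 1 TSH = (days from last Day 1 to last dose) + 30.
- Last dose on Day 1: 0 + 30 = 30 days.
- Epacadostat to the end of a 21-day cycle: 21 + 30 = 51 days, or 24 + 30 = 54 days with the 3-day window.

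The scheduled thyroid record would run about 30 to 54 days beyond the last Day 1 visit.

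**The case against.** The strongest reply is that nothing is broken. Table 4 sets the plan's own standard for thyroid monitoring, and the calendars meet it. Table 8 places safety measurement on Day 1 of each cycle, where TSH is drawn. The key laboratory parameters named in Section 12.3 are hemoglobin, neutrophils and platelets. All of this stands, so the point is an improvement and not a defect.

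Patients who stop for progression are also not left unwatched. The comprehensive examination at EOT includes the thyroid (4.9.1.2). Adverse event assessment is marked at EOT and again in the Survival Follow-Up column. Events above Grade 1 are followed to Grade 0–1 or new therapy (4.6.1). Unscheduled visits are allowed (4.7). Section 4.9.1.1 extends reporting of events of clinical interest to 100 days, although the list in 7.5.2 names only overdose and a liver-test pattern. These safeguards stand. None is a TSH, so they help least with change that has no symptoms.

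Three stronger readings are tempting, and the documents do not support them:
- **Section 4.5 contradicts itself, or a mandatory visit is missing from the calendar.** Sections 4.5 and 4.6.1 give the same timing of about 30 days, so EOT may simply be the Safety Follow-Up Visit. The second paragraph of 4.5 can be read as covering early departure from the study, and the ± 4 week scan window in footnote 9 fits a visit near day 30. The identity of the two visits is unstated, which is less than a contradiction.
- **The plan has no thyroid testing after treatment.** It does, at the 9-week visits, for those who attend them.
- **A day-30 TSH answers the warning about events months after the last dose.** It cannot detect what has not yet occurred.

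**Conclusion.** The point holds as a low-cost improvement. On either reading of EOT timing, patients who stop for progression have no scheduled TSH after their last Day 1 visit, and one added test changes that from zero to one. The benefit is confined to asymptomatic thyroid change up to about day 30. The primary PFS endpoint, the other efficacy endpoints, the significance level, power and sample size are untouched.

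The conclusion assumes that sites follow the calendars as printed and that the 30-day visit does not fall under the Follow-Up Visits column. That column is headed as 9-weekly, so the assumption is reasonable.

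A reader might want a count of affected patients. From the 6-month PFS rates in Section 12.1, 30 × (1 − 0.39) = 18.3 and 30 × (1 − 0.20) = 24.0 patients would have progressed or died by 6 months. This is only a rough guide to how common the route is. It includes deaths, ignores later progressions, and counts patients who may stay on treatment after progression (Section 10.3). It does not measure missed thyroid events, and the documents give no rate from which to estimate those.

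**What to change.** 1. In both Section 9 calendars, mark endocrine testing in the EOT column: TSH, with T3 and fT4 if TSH is abnormal or the patient has symptoms.
2. In Section 4.5, state that the EOT visit is the roughly 30-day Safety Follow-Up Visit of 4.6.1. If the two are meant to be separate, say so and schedule the TSH at the 30-day visit instead.

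Cost: one sentence and one cell per calendar, and one TSH assay per patient. That is at most 30 in the first course, plus one for each retreated patient and the occasional reflex T3 and fT4. If the visits are the same, the sample comes from a draw already scheduled for chemistry and hematology. If they are separate, the 30-day visit needs its own calendar entry and a blood sample. No visit is added either way.
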